#### **Abstract**

Smoking is becoming increasingly concentrated among individuals with the lowest levels of income, education, and occupational status. In fact, smoking rates in the United States among people living below the poverty line is nearly twice as high as those above the poverty threshold. Highly flexible and low burden technology-based treatment approaches may overcome many of the barriers that have limited the use and effectiveness of traditional smoking cessation treatments among low SES adults. Ecological momentary assessment (EMA), in which mobile devices are used to capture moment-to-moment experiences, allows for the measurement of phenomena in real-time within natural settings. Smartphone-based smoking cessation apps could offer easily accessible, highly tailored, and intensive interventions at a fraction of the cost of traditional smoking cessation counseling. The Smart-T app uses a lapse risk estimator to identify moments of heightened risk for lapse, and the algorithm tailors treatment messages in real-time based upon level of imminent smoking lapse risk and currently present lapse triggers.

#### **A. Specific Aims**

The primary long-term objective of this research is to reduce smoking rates among low SES adults. The next step towards this goal is to use a fully powered randomized clinical trial to compare the efficacy of the Smart-T app with the free and widely available National Cancer Institute (NCI) QuitGuide app for smoking cessation in the 26 weeks following a scheduled quit attempt. A total of 450 socioeconomically disadvantaged, treatment-seeking males and females will be randomly assigned to receive either the Smart-T intervention app or the QuitGuide intervention app. All participants will receive nicotine replacement therapy and complete EMAs, but only the Smart-T group will receive intervention messages that are tailored to the current level of lapse risk and current lapse triggers. The study aims are to:

**1. Determine the impact of treatment condition (i.e., Smart-T vs. QuitGuide app; n=225 per group) on biochemically verified smoking abstinence.**

*Hypothesis 1:* Participants randomly assigned to Smart-T will have significantly higher rates of biochemically-verified abstinence than those assigned to QuitGuide at 26 weeks post-quit.

**2. Determine the effect of Smart-T treatment messages on key lapse risk factors.**

*Hypothesis 2:* Smoking urge, stress, and cigarette availability will decline more and cessation motivation will increase more following tailored messages that target these lapse

triggers in real-time (Smart-T condition) compared with similar situations wherein no messages are provided (QuitGuide condition).

## B. Background and Significance

Smoking is the leading cause of preventable death in the U.S. and is implicated in an estimated 30% of all cancer deaths in this country. Recent studies indicate that smokers have average life expectancies that are 11-12 years shorter than those who have never smoked. Importantly, depending on the age that one quits, ex-smokers live up to a decade longer than those who do not quit. Although smoking prevalence has declined to 13.9% among U.S. adults who are not living in poverty, 26.1% of those living in poverty are current smokers. The prevalence of both poverty (16.6%) and smoking (21.1%) are greater in Oklahoma than in the US overall. More than a third of Oklahomans live in rural areas, and rural residence is associated with elevated smoking prevalence. Finally, Oklahoma is home to a large population of American Indians (12.9% of all residents), who have higher smoking prevalence (29.2% smoke) than other racial/ethnic groups.

Lower SES individuals are the fastest growing group of smartphone owners in the U.S. In fact, smartphone ownership has nearly tripled since 2011 to 67% in households earning less than \$30,000 per year. Furthermore, our recent work (August 2016; N=610) indicated that smartphone ownership is high even among homeless adults (56.1% have active smartphones). Smartphone-based smoking cessation apps could play a significant role in improving cessation rates for current and future generations of lower SES smokers. Smartphone apps could offer secure (e.g., data can be encrypted), easily accessible (i.e., smartphone owners report that their phones are within arm's reach for 90% of waking hours), highly tailored, and intensive interventions at a fraction of the cost of traditional smoking cessation counseling; thereby, overcoming many of the barriers that have hampered use of other empirically supported smoking cessation treatments among lower SES individuals. Furthermore, after being downloaded, smartphone apps can deliver tailored content (e.g., video, text) even when cellular reception and/or minutes/data are not available, overcoming some of the limitations of quit lines and texting based smoking cessation interventions (see).

Although there are hundreds of publicly available smoking cessation apps, few have been empirically evaluated using a randomized controlled trial design. In a content analysis of 252 available iPhone and Android apps for smoking cessation, Abroms and colleagues found that very few apps adhered to proven strategies for smoking cessation (e.g., suggesting use of effective medications, connecting to quit lines or clinics). QuitGuide is a free smartphone app developed by the Tobacco Control Research Branch at the National Cancer Institute (NCI) and based on content from Smokefree.gov. Unlike most available apps, QuitGuide's content adheres to established clinical practice guidelines, and includes features such as using motivational messages to encourage users to make a quit attempt, and detailed information about medications (e.g., nicotine replacement therapy; NRT). QuitGuide also enables and encourages users to track their mood, cravings, triggers, and lapses, and users can tag locations to receive support messages when they are in places they have deemed high risk for lapse. To date, only one study has examined the efficacy of the QuitGuide app. Bricker et al. compared QuitGuide to a smartphone delivered Acceptance and Commitment Therapy-based app (SmartQuit) in a randomized controlled trial. The overall quit rate for participants who were randomized to QuitGuide was 8%, compared with 13% for SmartQuit. Thus, there appears to be much room for improvement in phone-based treatments.

Ecological momentary assessment (EMA), in which handheld devices (e.g., smartphones) are used to capture moment to moment experience, allows for the measurement of phenomena

in real-time within natural settings. EMA data may facilitate a better understanding of the mechanisms involved in successful cessation attempts, those affecting smoking lapses, and those implicated in the transition from lapse to relapse. Our research team and others have identified momentary predictors of smoking cessation and smoking relapse (e.g., smoking urge, stress, easy cigarette availability, interacting with people who are smoking, alcohol use, cessation motivation). **These findings suggest that momentary changes in key variables may be tracked and potentially used to initiate interventions as they are needed.** Using smartphones to detect high relapse risk situations and automatically deliver tailored smoking cessation interventions may help socioeconomically disadvantaged smokers to avoid lapse and successfully quit smoking.

In summary, socioeconomically disadvantaged adults are less likely to quit smoking and are disproportionately affected by smoking-related morbidity and mortality. EMA studies have identified social, psychological, and environmental triggers that contribute to smoking lapse. To date, no interventions besides our recent pilot work (see **Preliminary Studies** section), have used EMAs to repeatedly assess current smoking lapse risk and automatically deliver tailored treatment content. Our preliminary work indicates that smartphones may be used to deliver automated, tailored, low burden, and easily accessible interventions to socioeconomically disadvantaged smokers, a population with substantial barriers that have hampered the use of traditional smoking cessation treatments. The proposed study would extend our previous work and determine if automated treatment content (e.g., messages focused on coping with lapse triggers, smoking cessation medication reminders) that is tailored to current situations can attenuate lapse risk.

### **C. Preliminary Studies/Progress Report**

Drs. [name] and [name] have used smartphones in 9 studies to collect EMA data for up to 6 months and influence health behavior in high-risk samples, including homeless (e.g., 1R01MD010733-01A1; PI [name]) and other socioeconomically disadvantaged adults (e.g., R01CA197314-01; PI [name]). In *Project Prevail*, EMA data were collected from smokers seeking treatment at a safety-net hospital tobacco cessation clinic ( $N=146$ ). Participants completed 83% of all EMAs. Using just 6 EMA variables (i.e., urge, stress, cigarette availability, alcohol use, motivation to quit, proximity to others smoking), we created a smoking lapse risk estimator that identified 80% of all smoking lapses within 4 hours of the lapse (false positive rate = 17%; see a detailed description of the development of the risk estimator here). In another study, we developed the *Smart-T* app that includes on-demand features (e.g., tips on coping with stress) and incorporates the *Prevail* lapse risk estimator to deliver tailored messages based on a person's momentary risk for smoking lapse. We examined the feasibility of the *Smart-T* app among smokers recruited from an urban safety-net hospital tobacco cessation clinic ( $n=59$ ). In that study, socioeconomically disadvantaged participants completed 87% of all EMAs and received an intensive level of tailored smoking-cessation treatment messages (102 messages on average) over a 3-week intervention period. We found that the on demand app functions were used regularly and the app was well-liked (e.g., 97% would like to use the app in the future if they were to relapse, and 85% would refer their friends who smoke to use the app). Analyses of EMA data revealed that urges to smoke were significantly reduced when tailored urge messages were delivered by the app, as compared to instances where other types of messages were delivered ( $p<.001$ ). We also found reductions in stress ( $p=.021$ ) and cigarette availability ( $p<.001$ ) following tailored stress and cigarette availability messages, compared to other types of messages. A total of 20% of participants were biochemically confirmed abstinent 12 weeks post-quit, which is better than many interventions conducted with low SES smokers. Finally, [name] is completing a 3-armed pilot randomized

clinical trial (i.e., Project Smart-T2; OUHSC IRB #7195) that compares the Smart-T2 app to standard in-person smoking cessation clinic care and the free NCI QuitGuide app. Smokers who attend a clinic based tobacco cessation program are randomized to groups and followed for 13 weeks (1 week pre-quit through 12 weeks post-quit). All participants are asked to complete EMAs on study provided smartphones for 5 weeks. To date, 64 participants have reached the 12-week post-quit follow-up visit. A total of 26% of Smart-T, 14% of QuitGuide, and 21% of in-person participants have achieved biochemically confirmed 7-day point prevalence abstinence at the 12-week post-quit visit.

#### **D. Research Design and Methods**

**Eligibility Criteria.** Participants (N=450) will be recruited through the TSET Health Promotion Research Center (HPRC) Tobacco Treatment Research Program (TTRP) which is directed by [name] (Co-I). Participants will also be recruited through advertisements (e.g. Facebook and Craigslist ads). Individuals seeking smoking cessation services at the TTRP will be given a verbal description of the study during their first visit, and those interested will be screened for study eligibility. Those who respond to study advertisements will complete a brief REDCap screener online (i.e., OKSmokerstudy.com), and those who qualify for the study will be contacted by study staff and scheduled for a screening/baseline visit. Consistent with our previous research with low SES populations, we have limited exclusion criteria so that the sample is as broad and representative of the population as possible. Interested individuals will be included in the study if they: 1) earn a score  $\geq 4$  on the Rapid Estimate of Adult Literacy in Medicine-Short Form (REALM-SF) indicating  $> 6^{\text{th}}$  grade English literacy level (required to complete EMAs; at least 88% of all individuals screened for our EMA studies have met this inclusion criterion), 2) are willing to quit smoking 7 days after the baseline assessment, 3) are  $\geq 18$  years of age, 4) have an expired CO level  $\geq 7$  ppm suggestive of current smoking for those who attend in person baseline visits or substantiate smoking status (e.g., produce a pack of cigarettes) during baseline assessments by sending picture of cigarettes to staff 5) are currently smoking  $\geq 5$  cigarettes per day, 6) have no contraindications to using NRT, 7) agree to complete EMAs and CO tests on a study provided or personal smartphone, 8) have household income  $\leq 200\%$  of the federal poverty guideline, and 9) agree to complete the 26-week post-quit follow-up assessment over the phone and via EMA. We will ask participants to verify their mailing address by showing (e.g., texting) a member of our study team a picture of their photo ID or a photo ID with a bill that was mailed to participant to verify their address. Those who are unable to provide a valid photo ID or piece of mail with their name and address will not be eligible to participate in the study. During the screener, a trained research assistant will confirm the participant's residency status, date of birth, University of Oklahoma employment status, and social security number with the participant. To be in compliance with IRS regulations, the University of Oklahoma must collect residency status for all participants. This determines how the payment is handled. All payments required to be reported as outlined in this policy require collection of the participant's name, tax identification number (SSN or ITIN), address, amount paid and source of funding for the payment.

**Participant Flow.** Individuals who provide informed consent and meet the study inclusion criteria will complete the baseline assessment in TTRP clinic space (the TTRP is located in [name] in a building that is adjacent to the PI's office) or via phone calls with study staff.

Following the baseline assessment, participants will be given instruction on how to complete phone-based EMAs and carbon monoxide assessments. All participants, regardless of

condition, will be compensated for completing the baseline assessments, phone based follow-up, and EMAs. In addition, participants will complete expired breath carbon monoxide tests using the portable iCO device 3 days per week (weeks 1-27).

**Study Overview.** Eligible and interested individuals will be randomized to 1 of 2 groups: 1) Smart-T smoking cessation intervention plus NRT, or 2) NCI QuitGuide smoking cessation intervention plus NRT. Stratified randomization will be used to assign participants to groups based upon race, sex, and cigarettes smoked per day. Participants will be followed for 27 weeks and will attend either 1 in-person visit or complete phone-based baseline visits. Participants will be prompted to complete daily EMAs and tests of smoking status using a portable, low-cost, carbon monoxide monitor (Bedfont iCO Smokerlyzer) on 3 days each week. This data will be used to address primary (i.e., biochemically verified 7-day point prevalence abstinence at 26 weeks post-quit) and secondary outcomes (e.g., 30-day point prevalence abstinence, number of days to first lapse, longest period of smoking abstinence). Geographic location data will be captured multiple times per day to link characteristics of the present environment (e.g., proximity to tobacco outlets) with cessation-related outcomes. We have already created software that integrates the iCO sensor into our Insight™ mobile application platform.

Participants who complete the in-person baseline visit will: 1) receive combination NRT (i.e., nicotine patch and gum/lozenge), and 2) complete EMAs daily on study provided smartphones. Participants who complete the remote baseline process will be mailed NRT, and a phone (if necessary) to complete EMAs. NRT has been shown to increase successful smoking cessation, and is currently offered via Quitline in all but 5 states. Combination NRT (patch + gum or lozenge) is considered a first line treatment, is relatively low-cost, can be kept on-site for easy distribution to study participants and is more effective than the patch or gum/lozenge alone. Consistent with over-the-counter package labeling, participants will be offered up to 10 weeks of nicotine patches (i.e., label dosage recommendations will be followed) and up to 12 weeks of nicotine gum or lozenges (i.e., participants will receive a 4 week supply of NRT at the completion of the baseline process and will be mailed NRT upon request for post-quit weeks 512).

Participants who own an Android smartphone (OS version 6.0 or higher) will be encouraged to download and use the study app on their own phone. Those who do not own this type of smartphone and those who do not have a data plan will be loaned a Samsung smartphone (or equivalent) for 27 weeks so that they may complete EMAs. Participants will navigate through the EMA program and enter data simply by touching the screen. The study app (i.e., Smart-T app or EMA only app) includes a “Call Staff” function/button that automatically calls study staff (e.g., if they have problems completing EMAs). The EMA app also includes a “Payment” button which, when pressed, indicates the number of EMAs that have been prompted and completed and the current level of compensation based upon the up-to-the-moment percentage of EMAs completed. Smartphones will automatically collect data when on-demand features are accessed for both the QuitGuide and Smart-T groups (e.g., number of times features are used). Use of personal vs. study provided phones will be examined as a covariate in all analyses.

Sub-Study: A sample (n=30) of American Indian/Alaska Native participants who have completed the 6 month follow-up assessment will be asked to participate in another qualitative interview designed to assess the perceived utility and cultural fit of the Smart-T App and NCI QuitGuide app. Information gathered from these qualitative interviews will be used to culturally modify and then experimentally test a new, culturally tailored, version of the apps for AI/AN smokers who want to quit smoking. In addition, this will serve as an incredibly valuable training opportunity for an emerging Native American scientist to learn tobacco cessation, mHealth, and qualitative methods research from an interdisciplinary team of leading experts in the field.

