### Description of Treatment Groups.

**NCI QuitGuide App + NRT Condition** The National Cancer Institute's QuitGuide app is a free smartphone app that is available on the Apple and Android app stores and has been downloaded by thousands of users. QuitGuide is one of the few apps that includes many of the recommendations detailed in the Clinical Practice Guideline. Individual level app feature use is accessible by request from the Smokefree.gov server (the PI has already obtained this type of QuitGuide data for a pilot study). The QuitGuide app aims to help smokers understand their smoking patterns and develop the skills needed to quit smoking. Participants who are randomly assigned to the QuitGuide condition will download the QuitGuide app and it will be set for a quit date 1 week following the baseline visit. QuitGuide provides content during the pre-quit period to prepare participants for their quit attempt. Participants will receive information on how to use QuitGuide app features. During the baseline process and will be encouraged to use the app for the duration of the study. QuitGuide features are listed in Table 1. Participants will be instructed to click "I Was Smoke Free Today" and the "I Slipped" tab to update their status every day (see Figure 1). Participants can use the on-demand "Track My Craving" tab to record and get help with managing cravings. They can click the "Manage My Mood" tab to track their mood and get tips on managing bad moods.

Participants can also personalize the app home screen with their list of reasons for quitting. Clicking the icon on the top right of the home screen will open a summary screen that will help participants to monitor their smoking cessation milestones and money saved by not smoking. Clicking the icon on the top left of the home screen enables modification of the quit plan; setting places and times of day when/where participants would like to receive app messages, and create journal entries. Participants can also click "My History" to examine their mood, urge, and lapse history. Lastly, participants may click "How to Quit" to learn more about ways they can improve their chances of successfully quitting (Figure 1).

[figure not shown]

Figure 1. QuitGuide app home screen

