Participants will use a study smartphone or their personal smartphone to complete assessments through an encrypted mobile application and all data will be automatically saved and sent to the study server. For those who receive study smartphones, the research staff will use a unique Google Play Store login to download the study app onto the phone. Passwords will only be known to research staff. At the conclusion of the participant's time in the study, participants will return the phone and all data collection through the Insight application will end. Study data will then be removed from the study phone. Participants who use their personal mobile device will receive an additional \$15 per month to offset data plan costs (if at least 50% of assessments are completed and contact details are confirmed) and will use their personal Google Play Store account to download the Insight app. At the conclusion of the participant's time in the study, the study data will be removed from the participant's phone and all data collection through the Insight application will end. Researchers will give participants instructions on how to delete the app from their personal device once they complete the study.

**6. Potential Benefits.** Potential benefits to participants include the use of study phones during the intervention period (at the current time, this benefit is estimated to be unlimited voice and text messages and 2 GB high speed data for the duration of their involvement in the study [i.e., 6 months]). Participants may also directly benefit from the FREE NRT and QuitGuide or Smart-T interventions (i.e., these interventions may reduce the likelihood of smoking lapse and relapse).

It should be noted that we also have given thoughtful consideration to the ways in which the design of this research may potentially limit the generalizability and specificity of conclusions drawn from it. We opted to use the mobile Bedfont iCO to determine smoking status rather than require participants to return to the clinic for in-person follow-up visits. This approach will reduce burden for socioeconomically disadvantaged smokers who may not have reliable transportation and will ensure we have biochemical verification of quit behavior, which is central to the present stage of research development. Overall, it is expected that the potential benefits to participants in the proposed study will outweigh potential risks.

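### The phone covariate is the phone actually used, which assignment could influence; adjusted arm comparisons should use phone status recorded before randomisation

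*Combined protocol and SAP*

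**What the plan says.** All of this is in the combined protocol and SAP.

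- **The covariate** (Section D, Study Overview): "Use of personal vs. study provided phones will be examined as a covariate in all analyses".
- **Who uses which phone** (same place): owners of a recent enough Android "will be encouraged to download and use the study app on their own phone". For everyone else: "Those who do not own this type of smartphone and those who do not have a data plan will be loaned a Samsung smartphone".
- **In-person participants** (same place, one paragraph earlier) are to "complete EMAs daily on study provided smartphones". This does not fit easily with the own-phone rule that follows.
- **Eligibility** (Section D) requires only that people "agree to complete EMAs and CO tests on a study provided or personal smartphone". It does not record which.
- **Apps by arm.** The study app depends on the arm: "The study app (i.e., Smart-T app or EMA only app". In the control arm, "Participants who are randomly assigned to the QuitGuide condition will download the QuitGuide app", and Table 1 marks EMA as an addition for this study. Downloads are described for people already assigned.
- **Payment** (Section G.5): "Participants who use their personal mobile device will receive an additional \$15 per month to offset data plan costs", conditional on at least 50% of assessments being completed.
- **Analysis** (Section E, Aim 1): the primary comparison is a chi-square or Fisher's exact test, with missed iCO assessments counted as not abstinent. Logistic regression is additional. Section E names enrolment/baseline type as a potential covariate and does not mention phone type.

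**The concern.** A covariate in a randomised comparison should be fixed before assignment, or at least be something assignment cannot move. The phone actually used is not clearly either. A qualifying owner may decline to use their own phone, and may do so after learning what has to be installed: one app in the Smart-T arm, two in the QuitGuide arm (QuitGuide plus the EMA-only app). The extra payment depends on completing assessments, so people who expect to stay engaged have more reason to use their own phone. Engagement also bears on the endpoint, because a missed iCO test counts as smoking.

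If phone choice depends on both arm and engagement, people using the same type of phone in the two arms are no longer alike in engagement. Adjusting for phone use then undoes part of the balance that randomisation gave. At stake are the adjusted supporting estimates, together with the analyst discretion left by saying only that the covariate will be examined.

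**Working it through.** **1. The plan's own figure.** Inputs (Section E): 18% vs 9%, 225 per arm, alpha 0.05, taken as two-sided.

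- Pooled rate 0.135. Null standard error = √(2 × 0.135 × 0.865 / 225) = 0.03222.
- Alternative standard error = √(0.18 × 0.82/225 + 0.09 × 0.91/225) = 0.03194.
- Power = Φ[(0.09 − 1.96 × 0.03222)/0.03194] = Φ(0.841) = 79.98%.

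The stated 80% reproduces. No covariate enters this calculation.

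**2. What adjusting for phone used can do.** Assumptions, not document figures:

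- 67% could use their own phone. This borrows the Background's smartphone ownership figure for low-income households.
- Half of participants are engaged. Abstinence is 14% in engaged and 4% in other participants, which averages 9%, in both arms (no true effect).
- Own-phone uptake among owners is 30% (other) and 70% (engaged) in QuitGuide, and 20 points higher, 50% and 90%, in Smart-T.

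Cells as fractions of each arm:

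| Arm, phone | Share | Abstinent | Rate |
|---|---|---|---|
| QuitGuide, personal | 0.5×0.67×0.3 + 0.5×0.67×0.7 = 0.335 | 0.1005×0.04 + 0.2345×0.14 = 0.03685 | 11.0% |
| QuitGuide, study | 0.665 | 0.09 − 0.03685 = 0.05315 | 8.0% |
| Smart-T, personal | 0.1675 + 0.3015 = 0.469 | 0.1675×0.04 + 0.3015×0.14 = 0.04891 | 10.4% |
| Smart-T, study | 0.531 | 0.09 − 0.04891 = 0.04109 | 7.7% |

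Both arms are at 9% overall, yet Smart-T is lower within each phone type. The Mantel-Haenszel odds ratio stratified by phone used is:

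- Numerator: 0.04891×0.29815/0.804 + 0.04109×0.61185/1.196 = 0.01814 + 0.02102 = 0.03916
- Denominator: 0.03685×0.42009/0.804 + 0.05315×0.48991/1.196 = 0.01925 + 0.02177 = 0.04103
- Ratio = 0.954, against a true value of 1.000.

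**3. Range.** The first four rows use the ownership and engagement assumptions above. The planned-effect column uses Smart-T abstinence of 28% and 8%, averaging 18%. The last two rows are logistic estimates with half of participants engaged.

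| Scenario (uptake: other/engaged) | Null odds ratio | Planned 9.0-point difference becomes |
|---|---|---|
| Same uptake in both arms, 30/70 | 1.000 | 9.0 |
| Smart-T +10 points | 0.977 | 8.7 |
| Smart-T +20 points | 0.954 | 8.4 |
| Extreme: QuitGuide 20/60, Smart-T 60/95 | 0.917 | 8.0 |
| 60% owners, abstinence 7%/20%, QuitGuide 50/90, Smart-T 90/90 | 0.984 | – |
| 70% owners, abstinence 5%/22%, QuitGuide 30/80, Smart-T 90/95 | 0.924 | – |

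Varying the engaged share from 30% to 70% gives 0.977 to 0.993 in the fifth row and 0.895 to 0.960 in the sixth. Swapping the two arms' uptake inverts each ratio: 0.954 becomes 1/0.954 = 1.048. The direction is therefore unknown.

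**4. Scale against sampling error.** At the planned rates the expected counts are 40.5 and 20.25 abstinent of 225. The standard error of the log odds ratio is √(1/40.5 + 1/184.5 + 1/20.25 + 1/204.75) = 0.29. The shifts ln(0.984) = −0.016 and ln(0.924) = −0.079 are about 0.06 and 0.27 standard errors.

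**5. Baseline phone status instead.** Ownership is fixed before assignment, so the engaged share among owners, and among non-owners, is the same in both arms. The null odds ratio is 1.000 in every scenario, including when the loaned group is pooled.

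**The case against.** The strongest reply is that the sentence does less than it appears to. It says the covariate will be examined, which is weaker than saying that every analysis will be adjusted. The primary test takes no covariates. The Aim 1 logistic regression and the Aim 2 regressions are described in terms of baseline characteristics. This stands.

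Three stronger readings are tempting, and the documents do not support them:

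- **That the primary result loses power.** A reader might put the shifted odds ratios into the 18% vs 9% calculation and conclude that power falls below 80%. The shift arises only in a model that contains the covariate. The planned test does not, so its power stays at 79.98%.
- **That phone choice is known to follow randomisation.** This is an inference from the arm-specific downloads. Ownership and data plan precede assignment and largely decide the variable. Read literally, the in-person sentence removes choice for that group. Encouragement and payment are the same in both arms, and Section D (Data loss prevention) reports under 1% of phones lost in most studies.
- **That pooling iPhone owners with people lacking a usable phone or plan causes bias.** It makes the covariate coarse and less prognostic. It does not bias a randomised comparison.

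It is also fair that no evidence is offered that two apps rather than one would alter uptake, and that the larger shifts need large gaps between arms. What the objection does not answer is that the covariate is defined by use, has no stated timing, and is named for all analyses.

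**Conclusion.** The point holds for adjusted analyses only. As worded, the plan invites adjustment of arm effects for a variable that assignment could influence, in the supporting logistic regression, the secondary outcomes, the GLMM and the Aim 2 models. Bias requires two things together: own-phone uptake that differs by arm, and a cause shared by uptake and outcome. The documents establish neither and exclude neither.

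Under the assumed inputs the null odds ratio is about 0.95 to 0.98 in moderate cases and about 0.92 in the harsher ones, or the reciprocals if uptake runs the other way. The binary-abstinence examples do not size any effect on the Aim 2 scores. The bias is probably small relative to sampling error, but it is avoidable. Sections D and E also disagree on which covariates are planned, and that needs settling in any case.

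**What to change.** Replace the sentence in Section D with:

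*Phone status recorded before randomisation (suitable Android with data plan: yes/no; optionally separating other smartphone owners from those with no usable phone or plan) will be the phone covariate in adjusted analyses. The phone actually used will be reported by arm and will not be adjusted for in arm comparisons.*

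Then:

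- State in Section E that the primary chi-square or Fisher test remains unadjusted, and list phone status beside enrolment type among the covariates for the adjusted models.
- Reconcile Section D's statement that in-person participants use study phones with its rule for owners of a suitable Android.

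**Cost.** The yes/no status is already needed to decide who is loaned a phone, but it must be recorded before assignment. The three-level version needs one extra screening item, because the loan rule does not require staff to separate iPhone owners from people with no phone, and it uses one extra degree of freedom. Sample size and the stated power do not change.
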